APPENDIX 2: FLOWCHART FOR SAFETY REPORTING

VIDAL Trial Protocol Page 11 of 45 Version 3, 25.07.2012

GLOSSARY OF ABBREVIATIONS

AE Adverse Event
AR Adverse Reaction
CI Chief Investigator
CRF Case Report Form

CRO Contract Research Organisation

CTA Clinical Trial Authorisation

CTIMP Clinical Trial of Investigational Medicinal Product

DBP Vitamin D Binding Protein

DMC Data Monitoring Committee

DSUR Development Safety Update Report

EC European Commission

EMA European Medicines Agency

EU European Union

EUCTD European Clinical Trials Directive
EudraCT European Clinical Trials Database

EudraVigilance European database for Pharmacovigilance

GAFREC Governance Arrangements for NHS Research Ethics

GCP Good Clinical Practice

GMP Good Manufacturing Practice
HES Hospital Episodes Statistics

IB Investigator Brochure
ICF Informed Consent Form

IMP Investigational Medicinal Product

IMPD Investigational Medicinal Product Dossier

ISRCTN International Standard Randomised Controlled Trial Number

IU International Units (1 μg = 40 IU vitamin D3)

JRO Joint Research and Development Office

MA Marketing Authorisation

MHRA Medicines and Healthcare products Regulatory Agency

MRC Medical Research Council

MS Member State

Main REC Main Research Ethics Committee

NHS R&D National Health Service Research & Development

PI Principal Investigator

QA Quality Assurance

VIDAL Trial Protocol Page 12 of 45 Version 3, 25.07.2012

QC Quality Control

QP Qualified Person for release of trial drug

RCT Randomised Control Trial
REC Research Ethics Committee
SAR Serious Adverse Reaction

SAE Serious Adverse Event

SDV Source Document Verification
SOP Standard Operating Procedures

SmPC Summary of Product Characteristics

SSA Site Specific Assessment

SSAR Suspected Serious Adverse Reaction

Subject An individual who takes part in a clinical trial

SUSAR Suspected Unexpected Serious Adverse Reaction

TMG Trial Management Group
TSC Trial Steering Committee

VDR Vitamin D Receptor 25(OH)D 25-hydroxyvitamin D

Note on units:

Vitamin D3: 1 μ g = 40 IU. A dose of 4,000 IU/day is thus 100 μ g/day. 25(OH)D (25-hydroxyvitamin D): 1 ng/ml = 2.5 nmol/L. A circulating level of 30 ng/ml is thus equivalent to 75 nmol/L.

KEYWORDS

Vitamin D, randomised trial, dietary supplement, longevity, survival

VIDAL Trial Protocol Page 13 of 45 Version 3, 25.07.2012

STUDY SUMMARY

TITLE Vitamin D and Longevity Trial (VIDAL): randomised feasibility study

DESIGN

Randomised controlled trial, with cluster randomisation of GP practices to either: (a) unblinded randomisation of open label vitamin D v. no treatment (800 people in 10 practices) or (b) double-blind randomisation of vitamin D v. placebo control (800 people in 10 practices). Within each practice, participants will be individually randomised to either vitamin D or control.

AIMS

- 1. To demonstrate the feasibility of a larger (n=20,000) randomized trial of prolonged vitamin D supplementation in people aged 65 to 84.
- 2. To provide estimates of cost and establish the study design and procedures required for the main trial for which this is a feasibility study.
- 3. To compare the effects of blinded versus open study design on trial recruitment and compliance.

OUTCOME MEASURES The main outcomes of the feasibility study are:

- Recruitment rates
- (ii) Treatment compliance
- Contamination rates (self-administration of >400 IU vitamin D per day (iii) or equivalent among controls)
- Attrition rates over 24 months (failure to attend GP practice for final (iv) assessment)
- Costs of placebo control versus open control study designs (v)
- Incidence of adverse events (severe and minor events) (vi)
- Assessment of infections, prescriptions and frequency of GP visits (vii)
- (viii) Assessment of blood 25-hydroxyvitamin D (25(OH)D) concentrations at recruitment and at two years in relation to potential determinants of vitamin D status including self-reported treatment compliance
- Assessment of change in systolic and diastolic blood pressure (ix)
- Cause-specific mortality and cancer incidence and hospital (x) admissions ascertained by flagging or tracing in national record systems, and reasons for any hospital admissions

POPULATION

1600 members of the general population registered with a General Practitioner's (GP) practice and aged \geq 65 years and \leq 84 years at enrolment.

PRINCIPAL ELIGIBILITY CRITERIA

- Age \geq 65 years and \leq 84 years at enrolment.
- Contactable by telephone and able to attend enrolment at the GP surgery, and able to give informed consent.
- Baseline corrected serum calcium ≤ 2.65 mmol/L

TREATMENT

- (i) Participants in double-blind practices will be randomised to receive either 100,000 IU monthly (average 3300 IU/day) of oral vitamin D3 (presented as 5 ml Vigantol® Oil) or double-blind placebo control (5 ml Miglyol® 812 Oil) monthly for 2 years: 800 participants
- (ii) Participants in unblinded practices will be randomised to receive either 100,000 IU monthly (average 3300 IU/day) of oral vitamin D3 (5 ml Vigantol® Oil) monthly for 2 years or open control (no treatment): 800 participants

[figure not shown]
DURATION Recruitment 1 year, treatment duration 2 years, study duration 3 years

VIDAL Trial Protocol Page 14 of 45 Version 3, 25.07.2012

STUDY FLOWCHART

Cluster randomisation within 10 matched pairs of GP practices between open randomisation with untreated controls, or double-blind randomisation with placebo control

Exclusions based on review of GP records:

[figure not shown]
Aged <65 or >84 years, no telephone, terminal illness, known active tuberculosis, referral for suspected hepatic or renal dysfunction, known sarcoidosis, hyperparathyroidism or nephrolithiasis, <3 years since remission from cancer (except non-melanoma skin cancer), taking >400 IU daily vitamin D, any other Investigational Medicinal Product (IMP) therapy within 4 months, concomitant carbamazepine, phenobarbital, phenytoin, primidone, digoxin, oral 1-alphahydroxylated vitamin D preparations (e.g. alfalcalcidol, calcitriol) or the combination of a thiazide diuretic (e.g. bendrofluazide, metolazone) with a calcium supplement

18,000 potentially eligible participants aged 65-84

Send description of appropriate trial and invitation to visit practice for informed consent, blood sample, blood pressure and lifestyle questions

Target enrolment: 1600 (9% of eligible participants)

Visit attended, signed informed consent taken, blood pressure measured, lifestyle questions completed, blood sample taken and aliquot stored, corrected serum calcium ≤ 2.65 mmol/L

At 24 months post-randomisation on all 1600 participants:

- (i) Repeat lifestyle questions, blood pressure measurement and blood sample to measure serum 25-hydroxyvitamin D concentration.
- (ii) Flagging for lifelong follow-up through national registers for death and cancer registration, and tracing through HES for hospital admissions and diagnoses.
- (iii) GP note abstraction: GP visits, prescriptions and infections over preceding 3 years.

VIDAL Trial Protocol Page 15 of 45 Version 3, 25.07.2012

1. INTRODUCTION

1.1 BACKGROUND

A consensus is emerging that circulating 25-hydroxyvitamin D (25(OH)D concentration the measure of vitamin D status) should be at least 75 nmol/l (30 ng/ml) for optimal health and increased life expectancy (Bouillon et al., 2005, Bischoff-Ferrari et al., 2006). Eighty percent of men and 87% of women aged over 65 years living independently in the UK have levels of 25(OH)D below 75 nmol/l (Hirani and Primatesta, 2005). Several epidemiological studies, notably the EPIC study of 1248 cases of colorectal cancer drawn from a population of more than half a million, report a correlation between low circulating 25(OH)D and the risk of developing various cancers (Giovannucci, 2005, Jenab et al., 2010, Lim et al., 2006). Low levels also correlate with reduced survival after cancer diagnosis, and cancer survival is improved among patients diagnosed in summer and autumn (when vitamin D status is highest) compared to those diagnosed in the winter (Lim et al., 2006). Giovannucci and colleagues suggested that the correlation between predicted 25(OH)D levels based on several risk factors (skin colour, obesity, latitude and physical activity) and total cancer incidence and mortality in their large cohort could be partly due to a direct effect of vitamin D (Giovannucci et al., 2006). A meta-analysis of studies of serum levels of 25(OH)D concluded that a daily intake of at least 1000 IU/day of vitamin D would substantially reduce colorectal cancer incidence (Gorham et al., 2007). Positive associations have however been reported between vitamin D status and risk of prostate cancer (Ahn et al., 2008) and pancreatic cancer (Stolzenberg-Solomon et al., 2010) highlighting the need for large randomised trials. Evidence on vitamin D and heart disease includes a nested case-control study in which men with 25(OH)D levels <37 nmol/l had a relative risk of myocardial infarction of 2.42 (95% CI= 1.53-3.84) relative to men with sufficient levels (>75 nmol/l) (Giovannucci et al., 2008). A systematic review suggested that optimal serum 25(OH)D for all endpoints should exceed 75 nmol/l (Bischoff-Ferrari et al., 2006) and that this can be achieved with doses of 1,800 to 4,000 IUs vitamin D per day without increasing health risks(Bischoff-Ferrari et al., 2010). Other effects of low circulating 25(OH)D may include compromised immunity (Cannell et al., 2006, Holick, 2007); we have previously demonstrated that the active metabolite of vitamin D induces antimicrobial activity in vitro (Martineau et al., 2007) and have performed a randomized controlled trial showing that vitamin D supplementation enhances immunity to mycobacteria (Martineau et al., 2007). These pleotropic effects are supported by experimental studies. The active metabolite of vitamin D, 1,25-dihydroxyvitamin D, suppresses proliferation and induces differentiation of cancer cells in vitro, and its receptor and the enzyme that synthesises it are both expressed in many cell types (Giovannucci, 2005).

A meta-analysis of published randomized trials on the effect of vitamin D on overall mortality (Autier and Gandini, 2007) showed a marginally significant reduction in overall mortality of 7% (95% CI 1%-14%: p<0.05). 82% of treated patients received vitamin D3 (cholecalciferol), the remainder vitamin D2 (ergocalciferol), either orally or by injection. Average daily doses ranged from 300 IU to 2,000 IU, the frequency of treatment ranged from daily to 4-monthly, and follow-up ranged from 6 months to 7 years. The meta-analysis included a British study of 2686 people aged 65-85 years randomised to 100,000 IU oral vitamin D3 or placebo every four months over five years (Trivedi et al., 2003). The authors' main recommendation was for large population-based randomised trials of prolonged vitamin D3 treatment at adequate dose, with total mortality as the primary endpoint.

The International Agency for Research on Cancer (IARC) Working Group on vitamin D and cancer, of which [name] was a member, reviewed the epidemiological evidence on vitamin D and cancer and concluded that the evidence was strong for colorectal cancer

but inconclusive for other individual cancers (IARC Working Group on Vitamin D, 2008) Their report concluded: "The only way to further address the cause-effect issue is to organise new randomized trials to evaluate the impact of vitamin D on all-cause mortality and on the incidence and mortality from common conditions including cancer. These trials should make sure that key parameters of vitamin D status (e.g., serum 25-hydroxyvitamin D levels before and in trial) can be assessed."

1.2 RATIONALE FOR CURRENT STUDY

The proposed regimen (100,000 IU monthly, equivalent to 3300 IU per day) is less than the current tolerable upper intake limit of 4000 IU/day for vitamin D in North America, defined as "the highest daily level of chronic nutrient intake that is likely to pose no risk of adverse health effects to almost all individuals in the general population" (Institute of Medicine, 2011). Indeed a risk assessment based on a review of clinical trial data concluded that a daily dose of at least 10,000 IU/day is safe (Hathcock et al., 2007), and the Institute of Medicine report accepts that this intake represents the NOAEL (no observable adverse effect level), which was adjusted for uncertainty to establish an upper limit of 4000 IU per day (Institute of Medicine, 2011).

The epidemiological evidence that various other vitamins prevent cancer has been disproved in randomized trials (Greenwald et al., 2007). Associations between inadequate vitamin D status and increased risk of cancer reported in the observational studies described above could also be at least partly due to confounding, and no adequately powered trial has tested vitamin D in doses that are high enough to achieve serum 25(OH)D concentration > 75 nmol/l. Although the majority of observational studies report associations between vitamin D deficiency and susceptibility to a range of pathologies, some studies are null, and a few report the opposite association; the existing evidence is thus not sufficient as a basis for a universal policy of high-dose vitamin D supplementation. Several investigators have recommended that randomized trials are needed to assess whether increases in circulating 25(OH)D can effectively decrease risk of disease, for example, colorectal cancer (Jenab et al., 2010) and heart disease (Giovannucci, 2009). The importance of trials of oral supplements of vitamin D is emphasized by the finding that in practice it is difficult for most people resident in the UK to obtain optimal vitamin D from sunlight or diet (Rhodes et al., 2010).

The main trial for which this is the feasibility study will be a randomized trial with 20,000 subjects aged 65-84 years treated for 5 years and followed for a further 5 years. A trial of that size will be needed to detect the 7% reduction that vitamin D supplementation might plausibly achieve in total mortality in healthy adults aged over 65 (Autier and Gandini, 2007). If self-administered vitamin D supplementation were shown to confer substantial health benefits it would be routinely recommended and widely adopted. This would also provide a rationale for a national policy of vitamin D supplementation for the general population, a review of the relative risks and benefits of sun exposure, and a revision of existing policy on vitamin D fortification of foods. If we show no benefit or unforeseen disadvantages this will also be a valuable contribution to knowledge.

An important public health priority is therefore to demonstrate the feasibility of a large randomized trial of prolonged vitamin D supplementation in older people, and to show that this will increase serum 25(OH)D to >=75 nmol/l in the majority of subjects. As well as demonstrating an expected increase in circulating 25-hydroxyvitamin D levels, the feasibility study will provide estimates of cost and establish the study design and procedures required for the main trial. An important feature of the feasibility study will be the comparison of a placebo control group with an open control group with no treatment. Randomized double-blind placebo-controlled trials are considered the gold standard, particularly where the endpoint is subjective, but an open control design may be

acceptable where the main endpoint is overall mortality. The primary purpose of this feasibility study is to ascertain recruitment levels, but the study will also include a cluster randomized comparison of the effects of placebo versus open control trial design on the reliability of self-reported infections and other adverse effects as well as on recruitment, participant acceptability and treatment compliance. The study will thus provide much needed evidence on an important methodological (and economic) issue in the design of pragmatic trials in preventive medicine.

2. STUDY OBJECTIVES

2.1 PRIMARY STUDY OBJECTIVES

The primary aim of the feasibility study is to establish the procedures required to conduct the main trial. We shall determine the recruitment rate and the compliance rate (the proportion adhering to allocated treatment over 2 years) in practices with placebo control, and in practices with open control. We shall also determine contamination rates in those allocated to placebo and those allocated to open control (ie self-administration of >400 IU vitamin D per day or equivalent). IMP adherence and use of additional vitamin D supplements will be studied both by self-report and from blood levels of 25(OH) vitamin D at entry and at 2 years.

2.2 SECONDARY STUDY OBJECTIVES

- (i) To compare costs of blinded and open label study designs, and hence to determine whether the extra costs of placebo control would be justified in the main trial.
- (ii) To provide unbiased data on the incidence of adverse events (vitamin D v. placebo control).
- (iii) To provide unbiased data on infections, prescriptions and frequency of GP visits (vitamin D v. placebo control), and to estimate the bias in these measures in participants allocated to vitamin D in an open control design.
- (iv) To analyse circulating 25(OH)D at recruitment and at 2-year follow-up in relation to allocated treatments and other potential determinants of vitamin D status, particularly self-reported sun exposure.
- (v) To analyse the change in systolic and diastolic blood pressure from recruitment to 2 years between vitamin D and control groups.
- (vi) To establish the feasibility of flagging for lifelong follow-up through national registers for death and cancer registration, and tracing through the Hospital Episodes Statistics database (HES) for hospital admissions and diagnoses.

3. STUDY DESIGN

This is a two year randomised controlled feasibility trial on 1600 people aged 65-84 comprising two study designs:

- (i) Blinded study: Participants in double-blind practices will be randomised to receive either 100,000 IU monthly (average 3300 IU/day) of oral vitamin D3 (presented as 5 ml Vigantol® Oil) or double-blind placebo control (5 ml Miglyol® 812 Oil) monthly for 2 years: 800 participants
- (ii) Open label study: Participants in unblinded practices will be randomised to receive either 100,000 IU monthly (average 3300 IU/day) of oral vitamin D3 (5 ml Vigantol® Oil) monthly for 2 years or control (no treatment): 800 participants

Twenty GP practices will be cluster randomised to either blinded or open label study design. We will identify 10 pairs of GP practices matched on region and socioeconomic

profile (deprivation score based on practice postcode) and randomly select one practice within each matched pair in which participants will be individually randomised between vitamin D and placebo, while participants in the other practice will be individually randomised between open-label vitamin D and open control.

3.1 STUDY OUTCOME MEASURES

3.1.1 Primary outcomes of the feasibility study

The primary aim of the feasibility study is to establish the procedures required to conduct the main trial: our target is to randomise 1,600 participants aged 65-84 through 20 GP practices.

Primary outcome measures:

- 1. The overall recruitment rate (the proportion of invited participants who are randomised) and comparison of recruitment rate in blinded versus open control studies.
- 2. The overall level of compliance with study medication and comparison of blinded medication versus open label vitamin D compliance (to evaluate whether participants taking open label vitamin D are more or less compliant than those who are unaware of IMP status). A randomized participant is defined as compliant:
- (i) If allocated to vitamin D: they report taking at least 19 (79%) of the 24 monthly doses of allocated IMP, and attend the 2-year follow-up visit.
- (ii) If allocated to no vitamin D (whether placebo or open control): they report taking a total of <300,000 IU of vitamin D supplements over the 2 years of the study, and attend the 2-year follow-up visit. (The current UK RDA of 400 IU/day is 292,000 IU over 2 years).

These will be combined as a single outcome measure, which is the number of people we must invite to get one person complying with allocated treatment, to demonstrate that the main trial is feasible. It equals the number invited divided by the number randomised and compliant.

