3.1.2 Secondary outcomes of the feasibility study

- (i) The overall level of attrition (failure to attend the final 2-year visit), and a comparison of attrition between open label and blinded practices.
- (ii) Costs of blinded versus open label study designs.
- (iii) Comparison of incidence of serious adverse events between vitamin D and control in blinded practices.
- (iv) Comparison between vitamin D and control of numbers of infections, GP prescriptions and GP visits (a) in blinded practices, and (b) in open-label practices. This will provide an estimate of the bias in these measures in participants allocated to vitamin D in an open control design.
- (v) Blood 25(OH)D concentration at recruitment and at 2 years in relation to allocated treatment and other potential determinants of vitamin D status (self-reported sun exposure, diet and use of vitamin D supplements).
- (vi) Comparison of change in systolic and diastolic blood pressure from recruitment to 2 years between vitamin D and control groups.
- (vii) Cause-specific mortality and cancer incidence will be ascertained by flagging in the National Health Service Information Centre (NHS IC).
- (viii) Hospital records will be collected by NHS number linkage with the Hospital Episode Statistics (HES) database.

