9.3 STATISTICAL ANALYSES

9.3.1 Main clinical analyses

The main analyses will be the matched-pair comparison of recruitment and overall compliance rates between blinded and open control designs. Details of additional vitamin D supplement use will be recorded at entry, and retrospectively at the 2-year final visit. Failure to report taking at least 19 doses of allocated IMP or to attend the 2-year final visit are included in the definition of non-compliance, so there will be no missing data for the main analyses.

Change in blood level of 25(OH)D from entry to exit will be analysed in relation to self-reported compliance. The effect of treatment on 25(OH)D level, both overall by allocated treatment and in compliant participants, will also be analysed in relation to the pre-treatment 25(OH)D level.

The principal economic issues in the feasibility study will be the overall additional trial costs in blinded practices, to be weighed against the advantages and disadvantages of placebo control in relation to possible bias in self-reporting of minor conditions and suspected side-effects, treatment compliance, and self-medication with vitamin D by controls. The feasibility of collecting appropriate resource use data will also be assessed, specifically the viability of linking HES data to NHS reference costs using Healthcare Resource Group (HRG) information in order to calculate NHS costs, and using participants' medical records to obtain information on the use of primary care services.

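### The primary comparison of blinded medication with open-label vitamin D scores placebo participants on supplement use, not on doses taken, and 9.3.1 states a different rule

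*Protocol*

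**What the plan says.** Protocol 3.1.1 names as the second primary outcome "The overall level of compliance with study medication" and a "comparison of blinded medication versus open label vitamin D compliance". The stated purpose is to learn whether people on open-label vitamin D are "more or less compliant than those who are unaware of IMP status".

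The definition that follows depends on allocation:

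- Vitamin D: compliant if "they report taking at least 19 (79%) of the 24 monthly doses of allocated IMP" and the 2-year visit is attended.
- Placebo or open control: compliant if "they report taking a total of <300,000 IU of vitamin D supplements over the 2 years of the study" and the 2-year visit is attended. Nothing is said about doses of oil.

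Section 9.3.1 explains why the main analyses will have no missing data. It says that "Failure to report taking at least 19 doses of allocated IMP or to attend the 2-year final visit" forms part of the definition of non-compliance, and it makes no exception for placebo. Section 6.1.1 lists placebo among the IMPs, with its own regimen of 24 doses.

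Under section 8, the quarterly follow-up asks everyone except open controls for the dates of their last three doses.

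**The concern.** The question in 3.1.1 is about taking the oil. In blinded practices both the vitamin D and the placebo participants are unaware of what they take, so both belong to the group that the question describes. Half of that group is scored on something else. A placebo participant who opens no bottle, avoids supplements and attends at 2 years is compliant, whereas a vitamin D participant with the same behaviour is not.

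The comparison can therefore show a difference when blinding has no effect on adherence, or hide one when it has. Sections 2.1 and 9.3.1 otherwise treat adherence to allocated treatment and self-medication by controls as separate matters, and this rule merges them. The result is meant to inform the choice between placebo and open control for a main trial of 20,000 people.

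In addition, 3.1.1 and 9.3.1 disagree on some placebo participants, so an analyst has to guess which rule governs a primary outcome.

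**Working it through.** **The protocol's own figures.** 19/24 = 79.2%, given as 79%. 400 IU × 730 days = 292,000 IU, just under the 300,000 IU limit. Both reproduce.

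**Inputs.** Arm sizes are 400 each (9.1), which is 40 per arm per practice with 10 practices per design. The protocol forecasts neither pass rate. Its only compliance figures are the illustrative 85% and 95% in 9.2, used below as one scenario. The other values are assumptions.

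**Built-in difference.** Let c be the proportion passing the dose rule, taken as equal in every arm that receives oil. Let s be the proportion of placebo participants passing the supplement rule. Both include attendance.

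- Open-label vitamin D: c
- Blinded vitamin D and placebo together: (c + s)/2
- Difference with no true effect: (c + s)/2 − c = (s − c)/2

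**Chance of a significant result.** Section 9.2 mentions a sign test on 10 pairs. Two-sided at 5%, it rejects when at least 9 of 10 pairs agree, so its exact size is 2 × (10 + 1)/1024 = 2.1%. Each pair compares 40 open-label vitamin D participants with 80 blinded ones. Ties are split and variation between practices is set to zero.

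| c | s | Blinded | Open-label | Spurious difference | Sign test significant |
|---|---|---|---|---|---|
| 80% | 95% | 87.5% | 80% | +7.5 | 54% |
| 85% | 95% | 90% | 85% | +5.0 | 30% |
| 85% | 90% | 87.5% | 85% | +2.5 | 7% |
| 90% | 95% | 92.5% | 90% | +2.5 | 10% |
| 90% | 85% | 87.5% | 90% | −2.5 | 11% |
| 85% | 85% | 85% | 85% | 0 | 2% |

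For the second row, the chance that one pair favours the blinded practice is 0.773, and 10 × 0.773⁹ × 0.227 + 0.773¹⁰ ≈ 0.30.

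**Conflict with 9.3.1.** The two sections classify a placebo participant differently only if that person attends, meets the supplement rule and reports fewer than 19 doses. At c = 85% and s = 95%, the share passing both rules lies between 85 + 95 − 100 = 80% and 85%. Those affected are then 95 − 85 = 10% to 95 − 80 = 15% of placebo participants, or 40 to 60 of 400.

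**Where the bias does not arise.** The 9.3.1 analysis compares overall compliance between designs. Each side is half vitamin D (dose rule) and half control (supplement rule). With equal adherence and supplement use, both sides equal (c + s)/2 and the difference is zero. The combined measure in 3.1.1 is built in the same way. Its level does depend on the rule: with about 9,000 invited and 800 randomised in blinded practices, c = 85% and s = 95% give 9,000/720 = 12.5 invited per compliant person, against 9,000/680 = 13.2 if placebo were judged on doses.

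**The case against.** The strongest reply is that the matched-pair comparison of overall compliance in 9.3.1 treats both designs alike and is free of this artefact. That is correct. A reader might infer that all the primary compliance results are compromised, and the documents do not support that. What remains is the separate comparison in 3.1.1, which the overall analysis cannot replace because it does not isolate oil-taking.

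Second, blinded medication could be read as blinded vitamin D alone, in which case the rules match and the artefact vanishes. The protocol never lists the arms. However, the stated contrast is with people unaware of their IMP status, and that describes placebo participants too. The ambiguity is itself a reason to name the arms.

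Third, the sentence in 9.3.1 may be shorthand. It leaves out the supplement rule and cannot apply to open controls, who receive no IMP. That is plausible, but it does apply on its face to placebo, and nothing marks it as partial.

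Fourth, the supplement rule is sensible for its other uses. For open controls, and for counting people who keep to their allocated exposure, avoiding vitamin D is what matters. This stands, and the rule should be kept there.

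**Conclusion.** The point holds for one primary comparison, blinded medication against open-label vitamin D, and for the mismatch between 3.1.1 and 9.3.1. The built-in difference is (s − c)/2, zero only when the two pass rates coincide. It is +5 points with the protocol's illustrative 85% and 95%, and ranges from −2.5 to +7.5 in the scenarios shown. It assumes that placebo is pooled into the blinded side and that dose-taking is the same in all oil-taking arms. The sign-test percentages also assume no variation between practices.

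Some stronger readings go too far:

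- A reader might infer that the bias always favours blinding. It reverses when s is below c.
- A reader might infer that the two sections disagree over the whole placebo arm, half of the blinded participants. They disagree only over placebo participants who attend, avoid supplements and report fewer than 19 doses.
- A reader might measure the gap against a 10-point design difference. The simulation in 9.2 concerns recruitment (10% v. 15%), and the 10-point figure is a supplementary power statement.
- A reader might see the scoring of deaths as non-attendance as a similar fault. That rule applies equally to both designs, deaths are also traced through national records, and the protocol gives no mortality rate from which to size an effect.

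**What to change.** In 3.1.1, name the arms in the comparison of blinded medication with open-label vitamin D. For that comparison, define compliance as at least 19 of 24 doses reported plus the 2-year visit in all three oil-taking arms: blinded vitamin D, placebo and open-label vitamin D. Alternatively, restrict it to blinded v. open-label vitamin D (400 v. 400), where the rules already agree. The first option answers the question as posed; the second leaves out placebo adherence.

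Keep the 300,000 IU rule for controls, reported as contamination and used in overall compliance and in the number invited per compliant participant. Reword 9.3.1 so that it states or refers to the same definitions and says which rule applies to placebo in which analysis.

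The cost is a few sentences in two sections. No new data are needed: dose dates are requested quarterly from every participant who receives oil and are checked against the packs at the final visit.
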